4.1 Summary description of the investigational device

Healsea® Chronic is a CE marked nasal spray composed with an hypertonic seawater solution (2.2% NaCl) and Symbiofilm® (0.02%). Symbiofilm® is a Lallemand proprietary marine postbiotic composition including an exopolysaccharide mainly composed of N-acetyl hexosamines, acidic and neutral monosaccharides.

Healsea® Chronic is a nasal spray indicated in adults over 18 years in the treatment of nasal symptoms of chronic sino-nasal conditions : allergic rhinitis, chronic sinusitis, and/or sensitive nose. It can be used also as post-operative nasal care after nasal surgery.

According to direction of use, one puff (1-2 sec) twice a day in each nostril is to be administered during 30 days or as recommended by the physician or the pharmacist.

The technical performances are summarized below:

Ingredient	Function(s)
Hypertonic Seawater solution 2.2%	
- Improve nasal mucosa function- Clean the nasal cavity and eliminate allergens and infectious agents
Symbiofilm®	
- Enhancing the cleansing efficacy- Reducing biofilm formation

Intended clinical performances in the intended destination are:

- Treatment of symptoms of chronic sino-nasal disorders: allergic rhinitis, chronic sinusitis and/or sensitive nose..
- It can be used also as post-operative nasal care after nasal surgery

4.2 Manufacturer

Healsea® Chronic is a class IIa Medical Device manufactured by Lallemand Pharma. CE marking has been obtained on 30 March 2021. The subcontractor for the manufacturing is AURENA, [name], Sweden.

4.3 Name or number of the model to permit full identification

The test device is named Healsea® Chronic. It is a nasal spray (150ml presentation), hypertonic seawater (2.2%) supplemented with Symbiofilm® (0.02%) identified by the code article: 75012DMMG

4.4 Traceability

Tracability of the Device will be achieved through the lot number (YYMMXXX, YY for year, MM for Month and XXX internal number of the manufacturer).

4.5 Intended purpose of the investigational device in the clinical investigation.

Healsea® Chronic will be used within its intended use in adult patients with CRS according to EPOS criteria [1].

4.6 Population and indications for which the device is intended

Healsea® Chronic will be used in the intended population (adults over 18 years) and within its intended indication (CRS) and according to the IFU.

4.7 Device Description

Healsea® Chronic is a nasal spray (available in 50 or 150mL) using the Bag-on-Valve (BoV) technology.

The BoV technology consists of an aerosol valve with a welded bag. The product is placed inside the bag while the propellant is filled in the space between bag and can. The product is dispensed by the propellant simply squeezing the bag when the spray button is pressed, the product is squeezed out of the bag by the compressed air/nitrogen, which creates the dispensing as a spray. Therefore, the product keeps its integrity, remaining separated from the propellant at all times. Compared to traditional aerosol spray technology, BoV has several benefits, for manufacturers, consumers and the environment. Packaging description of Healsea® Chronic is reported in Figure 1.

***The Spray Pin:** Packaging element ensuring the delivery of the product in the patient's nose.

***The Actuator:** Pacifica Spray actuator with a flow rate of 8ml/10s pressed enables the Propellant to squeeze the bag to dispense the product through the Spray Pin.

***The Valve assembly:** Packaging element ensuring the link between the bag and the actuator.

The Can: Standard aerosol aluminum can containing the bag and the propellant.

The Product: Hypertonic Seawater solution (2.2%) supplemented with Symbiofilm® (0.02%)

***The Bag:** FDA-approved laminated bag containing the product.

The Propellant: Because of the separation between product and propellant, BoV technology is used with compressed nitrogen filled between the can and the bag.

***Packaging element in contact with the product**

Figure 1- Packaging description of Healsea® Chronic

As summarized below, Healsea® Chronic is intended to be used on nasal mucosa. The duration of use is 30 days.

Type of contact	Device in contact with a surface
Type of tissues	Mucous membranes
Total duration treatment	It can be used for 30 days

4.8 Investigation Device Training/Experience

There is no need for specific training in using Healsea® Chronic.

An usability engineering process test according to the standard EN ISO 62366-1: 2015 was conducted with another product using BoV technology from the Healsea® range, Healsea® Children. Ten parents were recruited to ensure that the leaflet and the label were well understood and that the medical device was used correctly to ensure its safe understanding and use.

The analysis of the results demonstrates that:

- The information provided by the user interface is readable and understandable by participants: the information tested was easy to understand, without interpretation.
- The observations made during the simulations of use of the device have confirmed that all safety-related handling steps are properly followed, in accordance with the instructions given in the instruction for use.

Briefly, the adult to place the nozzle into the nostril while keeping head straight. Once the nozzle is placed, to press on the nozzle for 1-2 seconds in each nostril. To let flow the excess of solution, and wipe. To clean the nozzle with tissue, soapy water rinse and dry after use.

4.9 Reference to the IFU

The IFU of Healsea® Chronic is provided in Appendix A.

5. Justification for the design of the clinical investigation

Chronic rhinosinusitis (CRS) is an inflammation of the nose and paranasal sinuses and is characterized by two or more symptoms, one of which should be either nasal blockage/obstruction/congestion or nasal discharge (anterior/posterior nasal drip), lasting for 12 weeks or longer. In addition, facial pain or pressure and a reduction in the sense of smell can occur [1]. The condition can occur with or without nasal polyps.

The overall prevalence of symptom-based CRS in the population has been found to be between 5% and 12% [1].

The physiopathology of CRS is poorly understood with multiple environmental, host and microbial factors being implicated. Putative pathological factors include changes in the microbiota, imbalance of the local or systemic immune system, allergens, toxins and genetic predisposition [2].

A dysbiosis mechanism has been proposed as modulating inflammation in diseased sinuses. This hypothesis suggests that externally influenced changes in the nasal microbiome can result in dysbiosis, i.e. a shift from a “normal” or “healthy” microbial community structure and that this shift may be responsible for the initiation or maintenance of CRS. For example, the disruption of the commensal biofilm during a viral upper respiratory tract infection can create a niche for pathogenic species to grow [3]. Despite many contradictory statements in the different studies some common trends emerge. Less diversity in the microbial community rather than an increased overall bacterial load seems to characterize CRS compared to the healthy state with no consensus about specific genera indicative of disease [4], [5], [6]. However, anaerobes and *S. aureus* are found to be significantly more prevalent and abundant in CRS versus healthy controls [4]. Bacterial biofilm is detected on the sinus mucosa in up to 80% of CRS patients and its presence does not imply that it is causing mucosal inflammation. However, in the context of CRS, there are several possible mechanisms by which biofilms may be pro-inflammatory including the release of planktonic organisms and the release of superantigens, which can cause ciliary dysfunction and inhibition of ciliary clearance. Bacterial biofilms are likely a key modulator of the refractory nature of CRS [7].

Although clinical evidence from well-designed trials is scarce, European guidelines for chronic rhinosinusitis recommend daily nasal saline irrigation for reduction of the severity of symptoms of CRS [1]. A recent Cochrane analysis has concluded that daily nasal irrigation with hypertonic saline solution is more effective than placebo to improve patient symptoms [8]. The exact mechanisms by which nasal irrigation works are not known. However, most of the experts agree that it is primarily a mechanical intervention leading to direct cleansing of the nasal mucosa. Nevertheless, the efficacy of such solution remains moderate.

Healsea® Chronic is a CE marked medical device indicated in adults for the treatment of nasal symptoms of chronic rhinosinusitis. This is a seawater-based nasal spray supplemented with a natural Symbiofilm® extract (0.02%) isolated from marine bacteria. The nasal solution is hypertonic (NaCl 2.2%). Symbiofilm® is a marine postbiotic comprising active exopolysaccharides with emulsifying properties and *in vitro* antibiofilm activity. Antibiofilm properties have been demonstrated with the colorimetric microtiter plate assay [9]. In this model, a significant inhibition of *Staphylococcus aureus* and *Haemophilus influenzae* biofilms are observed. Detachment properties from human nasal epithelial cells of *Staphylococcus aureus* and *Pseudomonas aeruginosa* has also been demonstrated *in vitro*, suggesting an inhibition of biofilm formation at early stage in this model. Symbiofilm® has no bacteriostatic nor bactericidal activities.

To date, properly designed study to evaluate for the effect of topical therapies on microbiome are scarce so no definite conclusion can be made. In one study, use of saline irrigation with or without budesonide^{DCI} used was not associated with significantly distinct microbiota composition among either controls or post-operative CRS with polyp patients [10].

We design this exploratory study aiming at determining if the antibiofilm properties of Symbiofilm may modify sino-nasal microbiota, impacting α and/or β diversities. To this end middle meatus swab specimen will be taken from CRS patients before and after treatment with Healsea® Chronic. Bacteria colonization will be assessed using quantitative PCR and 16S rRNA gene sequencing.

6. Risks and Benefits of the Investigational Device and Clinical Investigation

6.1 Anticipated clinical benefit

Healsea® Chronic is a CE marked class IIa medical device indicated in the treatment of nasal symptoms of sino-nasal conditions of which CRS. The clinical benefit of nasal irrigation with saline solution used during several weeks to improve CRS symptomatology is well known. Due to its technical performances, Symbiofilm® may enhance the cleansing activity of the device.

6.2 Anticipated adverse device effects

The only anticipated adverse device effect is the feeling of itching and irritation while initiating the treatment with the medical device Healsea® Chronic. In case of such adverse reaction, the participant will be instructed to contact the investigator if wishing to stop the nasal spray use.

Furthermore, as mentioned in the IFU, patients with known hypersensitivity/allergy to any component of the test device will not be enrolled in the study.

6.3 Risks associated with participation in the clinical investigation

The collection of middle meatus specimen will be performed by the Principal Investigator or co-investigator who are familiar with this medical procedure. This additional procedure is invasive (MDCG 2021-6-Regulation (EU) 2017/745) but no expected risk is associated with this procedure. This procedure is definitely comparable to nasopharyngeal swab which is routinely performed for Sars-CoV-2 detections without safety concern. Furthermore, nasopharyngeal swabs were mentioned in the « Arrêté du 12 avril 2018 fixant la liste des recherches mentionnées au 2° de l'article L. 1121-1 du code de la santé publique » previously applicable for RIPH-2 with medical device. Additionally, in order to avoid any inconvenience, patients with defective access to the middle meatus, e.g. with deviated nasal septum, will not be enrolled (non-inclusion criterion) and a topical anesthesia with a lidocaine spray will be proposed to the eligible patients.

6.4 Possible interactions with concomitant medical treatments as considered under the risk analysis

No interaction is expected. Nevertheless, patient will be instructed to respect a 60-minute minimum interval after administration of the investigational medical device before administration of another nasal spray e.g. decongestant or mucolytics if prescribed.

6.5 Steps that will taken to control and mitigate the risks

In the line with *NF EN ISO 14971:2019* standard (Medical Devices – Application of risk management to medical devices), a risk analysis has been conducted to estimate the risks associated with each step of the device lifecycle. Most of the risk has been mitigated through product design and manufacturing.

The residual risk to patients who are administered this intervention is low. A list of potential risks associated with the device, procedures undertaken to minimise them and methods used for their management is described in the device Risk Management Process File.

Considering:

- The risk analysis (ISO 14971 activities) that demonstrates:
 - There is no longer High-level risk,
 - That, the 41 Medium risk level residual risks have an acceptable benefit-risk balance.
 - And all of the other residual risks (85) are at Low risk
- The fact that the device Healsea® Chronic can be considered as safe and effective according to the Clinical Evaluation Report,

the overall residual risk is acceptable and the benefit/risk ratio is considered satisfactory.

The verification of the implementation of risk control measures during life cycle phases of Healsea® Chronic is mainly performed by LALLEMAND PHARMA AG in compliance with the operating procedures currently used.

No specific risk for subject in participating in the study is identified, provided that the eligibility criteria are fulfilled. Thus the establishment of risk acceptability thresholds is assumed to be not necessary although it is a requirement from the ISO 14155:2020. Nevertheless, the safety and well being of subjects will be monitored throughout the study. Should a potential unanticipated risk be detected, the clinical investigation will be suspended, the risk assessment will be updated to adapt the risk control measures and the benefit-risk analysis.

6.6 Rationale for the benefit-risk ratio

Chronic rhinosinusitis is a painful disease that impacts the quality of life. Orbital and intracranial complications are rare but potentially serious.

Nasal saline irrigation are recommended by European and American guidelines as adjuvant treatment for CRS. The addition of Symbiofilm® to nasal saline irrigation may improve the clinical performances of the device. Furthermore, apart from feeling of itching and irritation while initiating the treatment, no adverse effect is anticipated.

The analysis of middle meatus swabs is expected to provide first insights on the *in vivo* mechanism of action of Healsea® Chronic. If an improvement of nasal microbiota is observed in the present study, this could justify to further study the impact of Symbiofilm® in a larger population of patients with CRS but also in other diseases with reported sino-nasal dysbiosis, e.g. asthma, especially in the paediatric population [12].

7. Objectives and hypothesis of the clinical investigation

7.1 Hypothesis

Our hypothesis is that a one month-course of Healsea® Chronic nasal spray could modify the sino-nasal microbiota diversity, impacting α and/or β diversities. Although performed on a small cohort of CRS patients, this clinical investigation is expected to provide first insights into the mechanism of action of Healsea® Chronic nasal spray *in vivo*.

7.2 Primary Objective

To characterize the change of sino-nasal microbial communities from adult CRS patients via 16S rRNA gene high throughput sequencing before and after 1-month treatment duration with Healsea® Chronic.

7.3 Secondary Objectives

- To assess the efficacy of Healsea® Chronic in improving health-related quality of life of CRS adult patients.
- To assess the global satisfaction of patients in using Healsea® Chronic nasal spray for CRS.
- Safety: to assess systemic and local tolerance of Healsea® Chronic over the study period.

7.4 Scientific justification and clinical relevance for effect sizes, non inferiority margins or equivalence

Not applicable. This is an exploratory clinical investigation.

7.5 Risks and anticipated adverse effects that are to be assessed

No specific risk for subject in participating in the study is identified, provided that the eligibility criteria are fulfilled. Expected and foreseeable side effects are feeling of itching and irritation while initiating the treatment. Nevertheless, the safety according to post market safety regulations (see paragraph 16) and well being of subjects will be monitored throughout the study.

8. Design of the clinical investigation

8.1 General

8.1.1 Design type of clinical investigation

This is an exploratory study, open label in one site, in France. No control group is deemed necessary at this stage.

8.1.2 Measures to be taken to minimize or avoid bias

Not applicable.

8.1.3 Primary Endpoint

Modifications in microbial load and/or profile

To determine the impact of Healsea® Chronic on the nasal microbiome, the microbial load will be evaluated by quantitative PCR and the microbiome taxonomic profiling by 16S rRNA gene sequencing. Data collected in patients before and after 1 month-treatment with Healsea® Chronic will be compared using statistical analyses to assess changes in microbial species abundance and diversity. Furthermore, special attention will be given to typical sino-nasal pathogens (e.g. *Staphylococcus aureus*, *Streptococcus pneumoniae*, *Haemophilus influenzae*, *Moraxella catarrhalis*) at genus level, and if reachable at species level.

8.1.4 Secondary Endpoints

To measure the clinical performance of Healsea® Chronic, the quality of life of CRS patients will be assessed with the Sino-Nasal Outcome Test 22 score (SNOT-22) [13]. This questionnaire is a disease-specific, quality-of-life-related measure of sinonasal function. Patients should rate sino-nasal symptoms and their impact from 0 to 5 where 0 means that there is no complaint and 5 means that there are serious complaints (Appendix B).

Patient satisfaction questionnaire assessing medical device usability, sensory perception and efficacy in using Healsea® Chronic for CRS (Appendix C).

Safety: Assessment of adverse events/incidents/expected side effects throughout the study.

8.1.5 Methods and timing for assessing, recording and analysing variables

8.1.5.1 Middle meatus swab specimen

Collection of middle meatus swab specimens will be performed at V1 and V2. A sterile stick swab (reference MW940; Medical Wire) will be introduced deeply within the middle meatus rotated at least 5 turns until visibly saturated. Immediately after collection, the swab will be placed in a dry tube (reference 62 554502; Sarstedt) and immediately stored in a freezer at -20°C.

8.1.5.2 SNOT-22

SNOT-22 (Appendix B) will be self-evaluated by the patient at V1 and V2 during the visit.

8.1.5.3 Assessment of sino-nasal microbial communities by 16S rRNA gene amplicon sequencing

DNA extraction

Genomic DNA (gDNA) is extracted using an optimized tissue-specific technique as previously described [14], [15]. This technique was carefully designed to maximize the recovery of bacterial DNA and to minimize any risk of contamination from the environment and the reagents. The quality and quantity of extracted gDNA are monitored by gel electrophoresis (1% w/w agarose in 0.5× TBE buffer) and NanoDrop 2000 UV spectrophotometer (ThermoFisher Scientific). All gDNA samples are stored at -20 °C until further processing.

Bacterial quantification by quantitative PCR (qPCR)

Total number of bacterial 16S rRNA gene copies is evaluated by real-time PCR amplification targeting the hypervariable regions V3-V4 with the primers: EUBF 5'-TCCTACGGGAGGCAGCAGT-3' and EUBR 5'-GGACTACCAGGGTATCTAACCTGTT-3'. The qPCR is realized in triplicate on a ViiA 7 PCR system (Life Technologies) using SYBR Green technology and the specificity of all qPCR products is assessed by systematic analysis of a post-PCR dissociation curve performed between 60°C and 95°C. The absolute number of copies of the 16S rRNA gene is determined by comparison with a quantitative standard curve generated by serial dilution of linearized plasmid standards.

Bacterial 16S rRNA gene sequencing

The V3-V4 hypervariable regions of the 16S rRNA gene are amplified by PCR using universal primer Vaiomer 1F (CTTCCCTACACGACGCTTCCGATCT-TCCTACGGGAGGCAGCAGT, partial P5 adapter-primer) and universal primer Vaiomer 1R (GGAGTTCAGACGTGTGCTTCCGATCT-GGACTACCAGGGTATCTAACCTGTT, partial P7 adapter-primer), which are fusion primers based on the qPCR primers with sequencing adapters. The first PCR reaction is carried out on a Veriti Thermal Cycler (Life Technologies) as follows: an initial denaturation step (94°C for 10 min), 35 cycles of amplification (94°C for 1 min, 68°C for 1 min and 72°C for 1 min) and a final elongation step at 72°C for 10 min. Amplicons (467 bp on the Escherichia coli reference genome) are then purified using the magnetic beads CleanNGS for DNA clean-up (CleanNA). A second PCR reaction for sample multiplexing is performed using tailor-made 6-bp unique index sequences with the forward primer Vaiomer 2F (AATGATA CGCG ACCACGAGATCTACACT-CTTCCCTACACGAC, partial P5 adapter-primer targeting primer 1F) and reverse primer Vaiomer 2R (CAAGCAGAAGACGGCATACGAGAT-index-GTGACT-GGAGTTCAGACGTGT, partial P7 adapter including index-primer targeting primer 1R). This second PCR step is run as follows: an initial denaturation step (94°C for 10 min), 12 cycles of amplification (94°C for 1 min, 65°C for 1 min and 72°C for 1 min) and a final elongation step at 72°C for 10 min. Amplicons are purified as described for the first PCR round. All libraries are pooled in the same quantity to generate an equivalent number of raw reads and are sequenced on a MiSeq Illumina platform (2 x 300 bp paired-end MiSeq kit v3, Illumina).

16S rRNA Gene Sequence Analysis

The targeted metagenomic sequences are analyzed using a bioinformatics pipeline based on 'find, rapidly, OTUs with Galaxy solution' (FROGS) guidelines [16]. In brief, after demultiplexing of barcoded Illumina paired reads, single-read sequences were cleaned and paired into longer fragments. OTUs are produced with single-linkage clustering. The taxonomic assignment is performed by BLAST against SILVA database to determine bacterial profiles from phylum to genus, and when reachable to species level. The following filters are applied: amplicons with a length of <350 nt or a length of

>490 nt are removed and OTUs with abundance lower than 0.005% and that appear less than twice in the entire dataset are removed. Alpha and beta diversity analyses are conducted on the OTU table.

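### The protocol specifies no product control and no PCR inhibition check, so spray residue on the V2 swab could be read as a change in the patient's microbiota

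*Protocol*

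**What the plan says.** **The device.** Protocol section 5: "This is a seawater-based nasal spray supplemented with a natural Symbiofilm® extract (0.02%) isolated from marine bacteria". Section 4.1 describes the extract as a composition including "an exopolysaccharide mainly composed of N-acetyl hexosamines, acidic and neutral monosaccharides". Residual DNA and microbial content are not given.

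**The assay (Protocol 8.1.5.3).** For load: "Total number of bacterial 16S rRNA gene copies is evaluated by real-time PCR amplification targeting the hypervariable regions V3-V4". The copy number is "determined by comparison with a quantitative standard curve generated by serial dilution of linearized plasmid standards". For profile: "The V3-V4 hypervariable regions of the 16S rRNA gene are amplified by PCR using universal primer Vaiomer 1F". The sequencing primers are built on the qPCR primers.

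**The checks described.** The extraction technique is designed to "minimize any risk of contamination from the environment and the reagents". In addition, "The quality and quantity of extracted gDNA are monitored by gel electrophoresis" and by spectrophotometer, a dissociation curve tests the specificity of the qPCR product, and OTUs are filtered on length and rarity. The text mentions no assay of the device, blank, spike-in, internal amplification control or dilution test.

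**Timing and comparison.** In Protocol 8.4.1 the V1 swab is listed before the device is handed over. V2 is the end-of-treatment visit, Day 30±5, with no interval set between last spray and swab. Section 8.1.3: "Data collected in patients before and after 1 month-treatment with Healsea® Chronic will be compared using statistical analyses". Section 8.1.1 states that no control group is needed, and 8.1.2 gives bias measures as not applicable. SAP 10.1 leaves the primary analysis to a separate document.

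**The concern.** The contamination statement covers the laboratory's own sources. The product is another possible source of bacterial 16S, and study exposure to it coincides with visit. Two artefacts can follow.

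- **Product DNA.** The assay does not separate device DNA from patient DNA. Product OTUs would count in total copies, alpha diversity, beta diversity and LEfSe at V2.
- **Inhibition.** Salt and polysaccharide on the V2 swab could slow the qPCR, so that copies read from a plasmid curve come out too low. Libraries are pooled in equal quantity, so any effect on the profile is indirect.

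A paired comparison removes what is constant within a patient. It does not remove something that arrives with treatment, and there is no comparator to show it. The hypothesis in Protocol 7.1 is that the device could modify alpha and/or beta diversity, and 6.6 says a favourable result could justify larger studies. Product DNA could imitate that result, and inhibition could imitate or hide a change in load.

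**Working it through.** The plan gives no load, effect size or power figure to reproduce, and the sample of 20 is declared arbitrary. The calculations below only bound the problem.

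**1. Extract applied per day** (0.02%; 1 mL taken as 1 g)
- SAP section 9: 45 g over 30 days = 1.5 g/day; × 0.0002 = 0.30 mg/day.
- Protocol 4.7 and 8.4.1: 8 mL per 10 s = 0.8 mL/s; × 1–2 s × 4 puffs/day = 3.2–6.4 mL/day, or 96–192 mL over 30 days. The upper end exceeds the 150 mL presentation in 8.2. One can allows at most 150/30 = 5 mL/day; × 0.0002 = 1.0 mg/day.
- The 45 g and the 96–192 mL do not agree, and the SAP prints 199.5 − 154 = 45 where its own theoretical weight is 154.5. These passages must be reconciled.

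**2. Product copies on a V2 swab**

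Assumptions, none from the documents: DNA is 1e-6 to 1e-4 of the extract; 0.1–1% of a day's dose is on the swab; 5 Mb genome; four 16S copies per genome.
- One genome: 5e6 × 650 / 6.022e23 g = 5.4 fg. One ng holds 1.85e5 genomes; × 4 = 7.4e5 copies.
- Low: 0.30 mg × 1e-6 × 0.001 = 3.0e-4 ng, about 2.2e2 copies.
- High: 1.0 mg × 1e-4 × 0.01 = 1.0 ng, about 7.4e5 copies.

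What this means depends on the patient's own load L, which is also not given. A share s of V2 reads needs L × s/(1 − s) product copies. For s = 10% that is about 1,100 copies if L = 1e4 and about 111,000 if L = 1e6.

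**3. Effect of a share s with the patient's community unchanged**

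Bray-Curtis V1 to V2 = s. Apparent load is multiplied by 1/(1 − s). For one new OTU, Shannon becomes (1 − s)H + h(s), with h(s) = −[s ln s + (1 − s) ln(1 − s)].

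| s (assumed) | Bray-Curtis | Load × | Shannon change, H = 2 | Shannon change, H = 1 |
|---|---|---|---|---|
| 1% | 0.01 | 1.01 | +0.04 | +0.05 |
| 5% | 0.05 | 1.05 | +0.10 | +0.15 |
| 10% | 0.10 | 1.11 | +0.13 | +0.23 |
| 20% | 0.20 | 1.25 | +0.10 | +0.30 |

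A small share hardly moves load, but a recurring new OTU is easy to detect. If it is absent at V1 and present at V2 in 6 patients, with no change the other way, an exact two-sided sign test gives 2 × 0.5^6 = 0.031. The plan does not name this test; it serves only as a yardstick. The filter for rare OTUs would not reliably remove an OTU that recurs across V2 swabs.

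**4. Effect of inhibition**

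At full PCR efficiency, apparent load is multiplied by 2^(−delay): 0.50 for one cycle (0.301 log10) and 0.25 for two. With 20 samples per visit and no true change, the approximate chance of p < 0.05 after a one-cycle delay is:
- rank-sum test as named in Protocol section 9 (n × 3/π): 46% at SD 0.5 log10, 15% at SD 1.0;
- paired comparison, within-patient correlation 0.5: 77% and 27%.

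The delay, SDs and correlation are assumed. Pairing makes the artefact more visible as a difference between visits and does not cancel it.

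**The case against.** **Controls may exist elsewhere.** Extraction follows two cited methods, and the primary analysis has its own document. Neither was available. A reader might infer that the laboratory runs no inhibition check and no blank. The documents do not support that; they show only that the protocol text commits to none.

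**The artefact may be trivial.** The extract is described as an exopolysaccharide composition, excess solution is wiped away, the swab is taken deep in the middle meatus, and V2 may fall days after the last spray. A reader might infer from the upper bound that product DNA would dominate V2. That is not supported: DNA content and carry-over are assumed, and no patient load is given to compare with.

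**V2 is not the only visit at risk.** The device was CE marked in March 2021, and Protocol 8.3.1.2 does not exclude earlier use of it or of similar sprays; irrigation is barred only during the study. Some V1 swabs may carry residue. The imbalance follows from the visit order but need not be complete.

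**The study is exploratory.** SAP 6.3.1 gives p-values for information only, and an unfamiliar marine genus might be noticed. This limits the consequence. It does not remove the bias from the descriptive results, and noticing an odd genus is not a planned control. It would also not reveal inhibition, or a taxon that resembles a resident one.

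**Conclusion.** The point stands as a missing control on the primary endpoint; it does not show that an artefact occurs. Following the protocol text alone, a change at V2 caused by device DNA or by inhibition cannot be told apart from a change in resident bacteria. The two push measured load in opposite directions and could mask each other. Inhibition bears mainly on the qPCR load, product DNA on both load and profile.

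The size is unknown and could be negligible. The range of about 2e2 to 7e5 product copies per V2 swab rests on the assumptions in step 2 and on one 150 mL can per course. Its width of about 3.5 orders of magnitude reflects how little the documents say about the product's DNA. Assaying the device would replace the assumed DNA content with a measurement.

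**What to change.** Add to Protocol 8.1.5.3, and carry into the separate microbiome analysis document:

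1. Run each device lot used, an unused swab wetted with product, an unused dry swab and an extraction blank through extraction, qPCR and sequencing with the study samples. The blanks are needed to tell product OTUs from reagent OTUs.
2. Flag OTUs that are present in the product libraries above a pre-set abundance and exceed their level in the blanks. Repeat load, alpha diversity, beta diversity and LEfSe without them as a sensitivity analysis. For load, multiply total copies by one minus the flagged share of reads. Leave the main analysis unchanged.
3. Run every extract neat and at 1:10 in qPCR. The expected shift is log2(10), about 3.3 cycles. If either sample of a patient departs from it by more than a pre-set tolerance, quantify both of that patient's samples at 1:10 and correct for the dilution. Treating the pair alike avoids a new difference between visits.
4. Record the time from the last spray to the V2 swab.

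**Cost.** A few extra libraries and qPCR wells, one extra recorded item, and no patient procedure. Lots are traceable (Protocol 4.4) and containers are returned (8.4.1). A resident taxon shared with the product is set aside in the sensitivity analysis only. Samples with few copies lose some precision at 1:10.
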